desired behaviors such as retention. CM, however, has not yet been tested or adapted for use in community-based programs for offender populations, particularly to encourage treatment admission and attendance.

The study will provide incentives to study participants for enrollment at the Walden House program and for attendance during the residential and the outpatient phases at Walden House. For a continuum of care model (such as that provided by CDCR), enrolling in community treatment is essential and increases the likelihood that clients will receive the benefits of treatment. In addition, increasing the amount of time that clients participate in residential and outpatient treatment is an important goal for improving outcomes. Only about 56% of clients referred from the SATF prison treatment programs to Walden House show up for admission, and the average length of attendance is 38 days. Increased enrollment would mean that a larger percentage of participants from prison-based treatment would be exposed to continuing treatment in the community, thereby improving the overall efficiency of CDCR's treatment system. Increased attendance would mean that clients have greater exposure to the treatment environment and treatment activities of the Walden House program, with the likelihood that this would improve post-treatment outcomes.

INTRODUCTION TO THE STUDY

The UCLA Integrated Substance Abuse Programs (ISAP), in collaboration with Walden House and the California Department of Corrections and Rehabilitation, is conducting a five-year health services research study that will involve a randomized test of the use of incentives to improve treatment utilization among parolees in community-based treatment. The incentives are in the form of vouchers that are redeemable for cash deposited into their Walden House bank account. The goals of the study are to increase the likelihood that prison treatment participants with a referral to community treatment will actually enroll in community treatment following release to parole and, once enrolled, will increase the amount of time that they participate in treatment. Increased exposure to community treatment as a result of incentives is expected to result in improved long-term outcomes of parolees who have participated in prison-based and community-based treatment.

The study has six specific aims:

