- (1) Determine whether offering an incentive (voucher) increases admission to community treatment by parolees who have participated in prison treatment.
- (2) For parolees who enter community treatment, determine whether providing incentives for attendance results in greater retention in treatment.
- (3) For parolees who enter community treatment, determine whether providing an incentive increases the likelihood that clients will participate in HIV testing and counseling.
- (4) Assess the long-term impact of the use of incentives on drug use, crime, and psychosocial outcomes at 12 months following the end of the five-month intervention.
- (5) Assess the long-term impact of the use of incentives to promote treatment participation on HIV risk behaviors at 12 months following the end of the five-month intervention.
- (6) Assess issues of acceptability, satisfaction, and sustainability of the use of incentives to increase admission and retention among staff and clients.

[figure not shown]
To accomplish these aims, the study design includes two phases: the Admission Phase and the Attendance Phase. In the Admission Phase, consenting clients at the Substance Abuse Programs at the California Substance Abuse Treatment Facility will be randomly assigned to the Admission Incentive group or to the Admission Information group. Upon release to parole, those in the Admission Incentive group who enroll in the Walden House treatment program will receive the voucher. In the Attendance Phase, which will last for five months, subjects from the

Admission Phase and other (SAP graduate parolees, non-SAP graduate parolees, In-Custody Drug Treatment Program [ICDTP] participants, and Post-Release Community Supervision participants [PRCS]) who enroll in treatment will be asked if they wish to participate in the Attendance Phase; if so, they will be consented and re-randomized to the Attendance Incentive group or to the Attendance Information group. Those in the Attendance Incentive group will be provided vouchers for attendance using an escalation/reset schedule.

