As required by Federal regulations (45 CFR86 46), any study involving human subjects must take care to protect the interests of the participants. We are proposing a randomized test of the use of a CM protocol with parolees to increase community treatment admission and retention, and thereby increase the likelihood of improved outcomes. A primary concern of ISAP will be to maintain the confidentiality of the data and identifying information of all persons who participate. Subjects for the study will be recruited by research staff from treatment participants at the Substance Abuse Treatment Facility prison who have volunteered for post-release aftercare at the Walden House Los Angeles Transitional Treatment Center. The research protocol and procedures for this study were approved by the UCLA General Campus Institutional Review Board (IRB) (which reviews socio-behavioral research), the Walden House IRB, and the state of California's Committee for the Protection of Human Subjects to ensure compliance with established guidelines on protection of human subjects and confidentiality. In addition, because this study involves prisoner research as defined by the Office for Human Research Protections (OHRP), a Prisoner Certification Letter and required study and IRB materials were forwarded to OHRP and OHRP assurance was obtained. The study also received a Certificate of Confidentiality from NIH protecting the study data from subpoena.

CHARACTERISTICS OF THE SUBJECT POPULATION

The sample for the study will be drawn from the population of treatment participants at the Substance Abuse Treatment Facility prison who volunteer for post-release aftercare at the Walden House Los Angeles Transitional Treatment Center and those who arrive at Walden House Los Angeles from other correctional facilities. All of the treatment participants at the Substance Abuse Treatment Facility prison and at the Walden House Los Angeles Transitional Treatment Center are adult males (18 years of age or older). According to program staff, all program participants are English-speaking.² At the program, stimulant dependence is the primary problem, with cocaine and methamphetamine being the most widely used drugs. All of the study participants will be parolees under the supervision of CDCR.

CRITERIA FOR INCLUSION OR EXCLUSION

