Study recruitment will take place in two phases. The first phase is the Admission phase that takes place at the Substance Abuse Treatment Facility prison. The second phase is the Attendance phase that takes place at the Walden House Los Angeles Transitional Treatment Center.

² A 1996 Federal law requires the deportation of non-citizen felons after their prison terms are completed. Therefore, WHLA draws from U.S. citizens only and program participants are fluent English speakers.

Admission Phase inclusion criteria:

The sample for the study will be drawn from the population of treatment participants at the Substance Abuse Treatment Facility prison who volunteer for post-release aftercare at the Walden House Los Angeles Transitional Treatment Center. In addition, subjects must be:

- At least 18 years of age
- English speaking
- Within 60 days of parole
- Able to provide informed consent to participate in the study
- Received a referral to the Walden House Los Angeles Transitional Treatment Center

Admission phase exclusion criteria:

- Potential subjects will be excluded from participating if they have serious cognitive problems that preclude their ability to provide informed consent or understanding of the questionnaire items, if they are a sexually violent predator or a child molester or if they have severe mental health problems.

Attendance phase inclusion criteria:

- Admission phase participant who arrived at the Walden House Los Angeles Transitional Treatment Center for treatment, or,
- Prison Substance Abuse Program (SAP) or non-SAP participant who arrived at the Walden House Los Angeles Transitional Treatment Center for treatment, or,
- In-Custody Drug Treatment Program (ICDTP) program participant who arrived at the Walden House Los Angeles Transitional Treatment Center for treatment
- Within 2 weeks after release
- At least 18 years of age
- English speaking
- Able to provide informed consent to participate in the study

Attendance phase exclusion criteria:

- Potential subjects will be excluded from participating if they have serious cognitive problems that preclude their ability to provide informed consent or understanding of the questionnaire items. Sexually violent predators, child molesters, and those with severe mental health problems are excluded from treatment at the Walden House Los Angeles Transitional Treatment Center as stipulated by the California Department of Corrections and Rehabilitation.

STUDY PROCEDURES

PROJECT TIMELINE

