- 7) interviewers administer the appropriate research documentation forms (see Assessment – Research Documentation Forms section)
- 8) interviewers look for reporting inconsistencies and socially desirable responses; and
- 9) consistency checks on reporting are built in as part of the interview process.

The Project Director will periodically sit in on interviews to ensure compliance with interview protocols and to identify problems that need correction. As a quality check, the Project Director will randomly call 10% of participants for whom interview forms are on file to verify that the interview took place and to ask about suggestions on interview procedures (see ISAP's data integrity policy in Appendix C).

RANDOMIZATION

In the Admission Phase, clients will be randomized to the Admission Incentive group or to the Admission Information group. Thus, each client has a 50/50 chance of gaining entry to the Incentive group or the Information group. Those clients in the Admission Phase who show up at Walden House and complete intake process will be consented and re-randomized to the Attendance Incentive group or to the Attendance Information group. In both cases, clients will

be randomly assigned to one of the study conditions using the Urn Randomization Program (version 1.10, developed at Yale University for Clinical Trials Network studies). Urn randomization is a procedure to maintain balance and minimization of bias across study groups for selected characteristics expected to be related to outcome (Stout, Wirtz, Carbonari, & Del Boca, 1994). The following baseline variables that are strongly associated with drug use and/or crime outcomes will be used in urn randomization:

- Race/ethnicity (African American vs. White/Hispanic/Other)
- Risk for recidivism (using the score on the Lifestyle Criminality Screening Form: 0-7 vs. 8-20)
- Parole status (In-Custody Drug Treatment Program vs. voluntary SAP graduate) – because custody arrangements differ between the two groups. In-Custody Drug Treatment Program (ICDTP) clients are considered to be in-custody and cannot leave the program premises without a staff member, while voluntary SAP graduates are not required to stay in the program.

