Aim 2 For parolees who enter community treatment, determine whether providing incentives for attendance results in greater retention in treatment.

H3. Participants in the Attendance Incentive group will have a longer length of time in treatment than will participants in the Attendance Information group.

Aim 3 For parolees who enter community treatment, determine whether providing an incentive increases the likelihood that clients will participate in HIV testing and counseling.

H4. Participants in the Attendance Incentive group will be more likely to agree to receive HIV testing and to participate in post-test counseling than will participants in the Attendance Comparison group.

Aim 4 Assess the long-term impact of the use of incentives on drug use, crime, and psychosocial outcomes at 12 months following the end of the six-month intervention.

H5. Participants in the Attendance Incentive group will be more likely to be abstinent than will participants in the Attendance Information group at the Month 12 assessment.

H6. Participants in the Attendance Incentive group will have a lower percentage of arrests and reincarcerations than will participants in the Attendance Information group at the Month 12 assessment.

H7. Participants in the Attendance Incentive group will have better psychosocial outcomes (employment, education, family relationships, psychological functioning, and HIV risk) than will participants in the Attendance Information group at the Month 12 assessment.

Aim 5 Assess the long-term impact of the use of incentives to promote treatment participation on HIV-risk behaviors at 12 months following the end of the six-month intervention.

H8. At the Month 12 assessment, participants in the Attendance Incentive group will report lower levels of injection drug use and engagement in HIV-risk sexual behaviors than will participants in the Attendance Comparison group.

H9. At the Month 12 assessment, participants in the Attendance Incentive group will report greater participation in HIV-related services (of any type) over the period since discharge from Walden House than will participants in the Attendance Comparison group.

Aim 6 Assess issues of acceptability, satisfaction, and sustainability of the use of incentives to increase enrollment and retention among staff and clients.

RQ1. Were clients and treatment staff who participated in the CM intervention accepting of and satisfied with the use of incentives to promote enrollment and attendance?

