The main approach to estimating treatment effects will be an intent-to-treat (ITT) analysis. This approach provides an unbiased estimate of the causal effect of random assignment (or the offer of treatment). But since there may be noncompliance and crossover from one group to another (despite the best efforts of the researchers to prevent it), the ITT approach does not provide an estimate of the causal effect of receipt of treatment, which is what treatment providers and policy makers are mainly interested in. If compliance is a problem, we will supplement ITT with an analysis that provides an estimate of the more clinically relevant Complier Average Causal Effect (CACE) (Dunn, Maracy, & Tomenson, 2005; Little & Yau, 1998). According to CACE methodology, owing to randomization, the proportion of compliers in the control group (an unobserved latent class) is, on average, the same as the proportion of compliers in the treatment group. The CACE represents a difference of outcomes between these two groups that is an unbiased estimate of the treatment effect among compliers.

OTHER ANALYSES

Additional analyses, while not testing specific hypotheses, will address related topics of interest, including, for example, responsiveness to the CM intervention by risk level and Anti-Social Personality Disorder, influence of motivation on outcomes, impulsiveness, time to dropout or rearrest, and predictors of levels of participation. OLS will be used to assess the association of participant characteristics with continuous dependent variables, and logistic regression will be used to assess the association of characteristics with binary variables. For date-based outcomes, Cox proportional hazards regression (Hosmer & Lemeshow, 1999) will be used to analyze elapsed time to a particular event (e.g., time to treatment enrollment or dropout, time to rearrest). This technique allows for the inclusion of covariates to control for any measured baseline differences between the groups. Although cell sizes may be too small to support strong conclusions about differential outcomes by subgroups (e.g., race/ethnicity, primary drug), subgroup findings may suggest either refinements in the protocol or hypotheses to be considered in future studies.

QUALITATIVE ANALYSES

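### The primary retention test (H3) pools in-custody ICDTP clients with voluntary clients and ignores the custody factor used in randomization, so it may understate the voucher effect in clients free to leave

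*Protocol*

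**What the plan says.** All places are in the Protocol.

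- **Eligibility.** Criteria for Inclusion or Exclusion admits to the Attendance Phase an "In-Custody Drug Treatment Program (ICDTP) program participant who arrived at the Walden House Los Angeles Transitional Treatment Center for treatment". Introduction to the Study describes the entrants as Admission Phase subjects and "other (SAP graduate parolees, non-SAP graduate parolees, In-Custody Drug Treatment Program [ICDTP] participants", and also Post-Release Community Supervision (PRCS) participants.
- **Custody.** Randomization says: "In-Custody Drug Treatment Program (ICDTP) clients are considered to be in-custody and cannot leave the program premises without a staff member". It contrasts these clients with volunteers from the prison program, who are free to leave, and gives this difference as the reason for making parole status an urn factor, with two levels: ICDTP and voluntary SAP graduate.
- **Population description.** Characteristics of the Subject Population says: "All of the study participants will be parolees under the supervision of CDCR".
- **Hypothesis.** H3 under Primary Aims reads: "Participants in the Attendance Incentive group will have a longer length of time in treatment than will participants in the Attendance Information group". Retention is one of the two outcomes for which the study is powered (Power Analysis).
- **Test.** Hypothesis Testing starts with t-tests and chi-square tests at a two-sided .05 level. Under Design Analyses, a covariate is used only if it differs significantly between arms and then also predicts group membership in a logistic model.
- **Differential response.** Other Analyses names risk level and Anti-Social Personality Disorder, and mentions "differential outcomes by subgroups (e.g., race/ethnicity, primary drug" as examples. Custody status is not named.

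**The concern.** H3 asks whether vouchers make clients stay longer. The problem behind it is early leaving: for clients referred from the prison programs, "the average length of attendance is 38 days" (Conception of the Problem Addressed). A client who may not leave unaccompanied has less room to respond on that outcome, whichever arm he is in. The protocol knows this, since it balances on the factor for this reason, but its stated test makes no use of it.

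Urn balancing prevents confounding by custody status. It does not prevent dilution: if in-custody clients respond less, the pooled difference is an average of a larger and a smaller effect. It also makes a significant imbalance unlikely, so the covariate rule will probably leave out a factor expected to be strongly related to length of stay. A small or null pooled result would then be ambiguous for clients who are free to leave, and a later split by custody status would be post hoc.

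**Working it through.** **Inputs.** N = 200 in the Attendance Phase, two-sided alpha .05, no attrition for retention (Power Analysis and Hypothesis Testing). 50/50 allocation gives 100 per arm. The protocol gives neither the in-custody share f nor the voucher effect in custody; both are assumptions here, and a common SD is assumed.

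**Step 1: the plan's own figure.** The smallest effect detectable with power .80 is d = (1.96 + 0.84) × √(2/100) = 0.396, or 0.398 by the exact t-test. At d = 0.40 power is .80, and at d = 0.50 it is .94. The claim that 200 clients suffice for a low-medium effect reproduces.

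**Step 2: dilution.** Let in-custody clients have a fraction r of the effect d seen in the others. The pooled effect is d × [1 − f(1 − r)]. With d = 0.40 and 100 per arm (t-test):

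| Share f | Response in custody | Pooled effect | Power |
|---|---|---|---|
| 0 | – | 0.40 | .80 |
| 20% | none (r = 0) | 0.40 × 0.80 = 0.32 | .61 |
| 30% | none (r = 0) | 0.40 × 0.70 = 0.28 | .50 |
| 20% | half (r = 0.5) | 0.40 × 0.90 = 0.36 | .72 |
| 30% | half (r = 0.5) | 0.40 × 0.85 = 0.34 | .67 |

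For a larger effect of d = 0.50 with no response in custody, power is .81 and .70 at 20% and 30% (normal approximation).

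**Step 3: is 20–30% a plausible range?** The planned 250 Admission Phase clients at the stated 56% show-up give 140 arrivals. If vouchers raise the incentive arm to about 73%, arrivals are 125 × 0.56 + 125 × 0.73 ≈ 161. If all consent, 39 to 60 of the 200 (20–30%) come from all other sources together, and ICDTP is only one of these. If only 80% of the 140 consent, 112 remain and the other sources supply 88 of 200 (44%). So 20–30% is an upper range under full consent and not an estimate of f.

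**Step 4: would testing only clients not in custody be better?** With 80 or 70 per arm at d = 0.40, power is .71 or .65. That beats the pooled test only if in-custody clients hardly respond (.61, .50). With half the response the pooled test does at least as well (.72, .67).

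**Step 5: what adjustment does.** Putting status in the model does not undo dilution; it removes the variance due to different mean stays. If in-custody stays were longer by one SD (assumption, no response in custody), the unadjusted pooled test has power .55 and .43 at f = 20% and 30%. Adjustment restores about .61 and .50.

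**Step 6: precision by custody status.** In SD units, the 95% half-width is 1.96 × √(2/n) for n per arm. With f = 20% it is 0.62 in custody (n = 20) and 0.31 otherwise (n = 80). The interaction has standard error √(2/20 + 2/80) = 0.354, so a true difference of 0.40 is detected with power of about Φ(0.40/0.354 − 1.96) = .20.

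**The case against.** **No response in custody is only a worst case.** Being unable to leave is not the same as attending. What Constitutes Attendance requires the full clinical day for residential clients, the endpoint counts days of attendance, and the schedule runs on into outpatient weeks. This stands, and it is why half the response is shown beside none. It is weakened by Attendance Documentation, where the daily record rests on the bed check sheet, which a client who may not leave will usually satisfy.

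**The size is not derivable.** This stands. The share, the length of custody and the response in custody are all unstated, and at d = 0.50 the loss is smaller.

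**Stratified analyses belong in an SAP, and the lists in Other Analyses are only examples.** This stands in part: not naming custody status there is not an error in itself. But the protocol does fix the unadjusted first test and the covariate rule, and these pass over its own randomization factor.

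**Stronger readings that the documents do not support.** A reader might infer that a null H3 result could not be interpreted at all. It could: status is recorded and balanced, so the comparison as assigned is valid for the population enrolled. A reader might also infer that the description of all participants as parolees is false. The protocol never says that ICDTP clients are not parolees, and it calls the factor parole status. The wording is unreconciled, most visibly where Introduction to the Study lists ICDTP and PRCS participants beside the parolee groups. Finally, a reader might want the Aim 2 conclusion to rest on voluntary clients alone. Aim 2 concerns parolees who enter community treatment, and that change would replace the primary analysis with a subgroup whose power advantage depends on almost no response in custody.

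**Conclusion.** The concern holds as a weakness in how H3 is analyzed and described, and does not make the test invalid. The protocol pools clients whose stay is constrained with clients who may leave, and its stated test is likely to ignore the factor that separates them. If in-custody clients respond less, the pooled estimate understates the effect in the others. In the illustration at d = 0.40, the power loss runs from 8 points (.80 to .72: 20% share, half response) to 30 points (.80 to .50: 30% share, no response). These figures rest on an assumed share, an assumed response and a common SD; the true loss may be smaller, and could be larger if the share exceeds 30%. The change is worth making because H3 is one of the two primary aims and the factor is already recorded.

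**What to change.** 1. Keep eligibility, the urn factor and the pooled as-assigned comparison as the primary H3 analysis, but include custody status in the H3 model whether or not it is imbalanced at baseline.
2. Pre-specify as supportive the H3 estimate with 95% CI by custody status (ICDTP against not in custody), plus the arm-by-status term. State where non-SAP and PRCS clients fall, since the urn factor has no level for them.
3. Reconcile the population wording across Introduction to the Study, Characteristics of the Subject Population, Criteria for Inclusion or Exclusion, and Randomization.
4. Report the custody mix by arm alongside H3.

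The cost is some wording and one model, largely on data already entered for randomization; non-SAP and PRCS clients need a defined code. The downside is wide intervals by custody status and low power for the interaction, so these estimates should be read as description and not as a second primary test.
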